8.2.4. Samples for Immunogenicity Research

Blood samples for immunogenicity testing will be collected to determine antibody production against LY3164530. Immunogenicity will be assessed by a validated assay designed to detect anti-drug antibodies (ADAs) in the presence of LY3164530 antibodies may be further characterized and/or evaluated for their ability to neutralize the activity of LY3164530. The presence of ADAs and neutralizing ADAs may be compared to any changes in expected PK/PD parameters. In the event of any AE suspected of being related to immunogenicity, the presence of ADAs may also be evaluated. A portion of the sample taken for immunogenicity testing may be used for PK analysis, in the setting of infusion-related reactions.

Samples may be stored for up to a maximum of 15 years following last patient visit for the trial at a facility selected by the Sponsor to enable further analysis of immune responses to LY3164530. The duration allows the Sponsor to respond to regulatory requests related to LY3164530.

8.3. Efficacy Evaluations

A secondary objective of the study is to document any antitumor activity. Refer to [Attachment 1](#) for details regarding the timing of specific efficacy measures.

Each patient will be assessed by one or more of the following radiologic tests for tumor measurement:

- Computed tomography (CT) scan
- Magnetic resonance imaging (MRI)

Each patient's full extent of disease will also be assessed with:

- Tumor measurement by RECIST 1.1 (Eisenhauer et al. 2009)
- Evaluation of tumor markers, if indicated
- Evaluation of the ECOG performance status.

In rare circumstances, historical radiologic exams for RECIST criteria that are obtained greater than 28 days prior to the first dose may be used, but this decision must be discussed with the Sponsor and documented in writing.

To confirm objective responses, all lesions should be radiologically assessed, and the same radiologic method used for the initial response determination should be repeated at least 4 weeks following the initial observation of an objective response, using the same method that was used at baseline. If a patient is discontinued from the study, repeat radiology assessments may be omitted if clear clinical signs of progressive disease are present.

8.4. Procedure/Sampling Compliance

Every attempt will be made to enroll patients who have the ability to understand and comply with instructions. Noncompliant patients may be discontinued from the study.

The collection times of safety assessments, PK samples, PD samples, and efficacy measurements are given as targets, to be achieved within reasonable limits. The scheduled time points may be subject to minor alterations; however, the actual collection time must be correctly recorded on the eCRF and lab requisition form.

The scheduled collection times may be modified by the Sponsor based on analysis of the safety and PK information obtained during the study. Any major modifications that might affect the conduct of the study, patient safety, and/or data integrity will be detailed in a protocol amendment.

9. Data Management Methods

9.1. Data Quality Assurance

To ensure accurate, complete, and reliable data, Lilly or its representatives will do the following:

- provide instructional material to the study sites, as appropriate
- Sponsor start-up training to instruct the investigators and study coordinators. This session will give instruction on the protocol, the completion of the eCRFs, and study procedures
- make periodic visits to the study site
- be available for consultation and stay in contact with the study site personnel by mail, telephone, and/or fax
- review and evaluate eCRF data and/or use standard computer edits to detect errors in data collection
- conduct a quality review of the database.

In addition, Lilly or its representatives will periodically check a sample of the patient data recorded against source documents at the study site. The study may be audited by Lilly or its representatives and/or regulatory agencies at any time. Investigators will be given notice before an audit occurs.

To ensure the safety of participants in the study, and to ensure accurate, complete, and reliable data, the investigator will keep records of laboratory tests, clinical notes, and patient medical records in the patient files as original source documents for the study. If requested, the investigator will provide the Sponsor, applicable regulatory agencies, and applicable ERB(s) with direct access to the original source documents.

9.2. Data Capture Systems

9.2.1. Case Report Form

An electronic data capture system will be used in this study. The site maintains a separate source for the data entered by the site into the Sponsor-provided electronic data capture system.

For data handled by a data management third-party organization (TPO), eCRF data and some or all data that are related will be managed and stored electronically in the TPO system. Subsequent to the final database lock, validated data will be transferred to the Lilly data warehouse, using standard Lilly file transfer processes.

For data handled by the Sponsor internally, eCRF data and some or all data that are related will be managed by the Sponsor and stored electronically in the Sponsor's system.

9.2.2. Ancillary Data

Data managed by a central vendor will be stored electronically in the central laboratory's database system. Data will subsequently be transferred from the central vendor to the Lilly generic labs system and the TPO's system.

Bioanalytical data will be stored electronically in the bioanalytical laboratory's database. Data will subsequently be transferred from the bioanalytical laboratory to the Lilly generic labs system and the TPO's system or directly to Lilly.

Electrocardiogram data will be stored electronically in the central database system of Lilly's central review organization. Data may subsequently be transferred from the central review organization system to the TPO's system.

Data from complaint forms submitted to Lilly will be encoded and stored in the global product complaint management system.

10. Data Analyses

10.1. General Considerations

Statistical analysis of this study will be the responsibility of Lilly.

The interpretation of the study results will be the responsibility of the investigator with the Lilly CRP/CRS, pharmacokineticist, and statistician. The CRP/CRS and statistician will also be responsible for the appropriate conduct of an internal review for both the final study report and any study-related material to be authorized by Lilly for publication.

The analyses for this study will be descriptive, except for possible exploratory analyses as deemed appropriate. Data analyses will be provided by dose levels and for all patients combined wherever appropriate. For continuous variables, summary statistics will include number of patients (N), mean, median, standard deviation, standard error (SE), minimum, and maximum. Categorical endpoints will be summarized using N, frequency, percentages, and associated SE. Missing data will not be imputed. Exploratory analyses of the data that are not described in the protocol will be conducted as deemed appropriate.

This is a Phase 1 study with an open-label, dose escalation design. Patients will be enrolled into cohorts sequentially without randomization to dose level. During dose escalation, the total sample size per cohort will be guided by the mTPI method and determined by the occurrences of DLTs (up to 20 patients per cohort before establishing the RP2D and schedule). The total sample size is anticipated to be approximately 50 patients.

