5.2. Objectives

5.2.1. Primary Objective

The primary objective of this study is to determine an RP2D and schedule of LY3164530 that may be safely administered to patients with advanced or metastatic cancer.

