6.2. Summary of Study Design

Study JNBA is a multicenter, nonrandomized, open label, dose escalation Phase 1 study of IV LY3164530 in patients with advanced and/or metastatic cancer. Eligible patients will receive LY3164530 as an infusion on Days 1 and 15 (Schedule 1) or on Days 1, 8, 15, and 22 (Schedule 2) of each cycle. A cycle will consist of 28 days and the schedules will enroll in parallel.

Dose escalation will be driven by a modified toxicity probability interval (mTPI) method. The RP2D and schedule will be determined once at least 10 patients, but no more than 20, are treated at a dose and schedule that is at or below the maximum tolerated dose (MTD). The actual sample size for Study JNBA is anticipated to be approximately 50 patients depending on the incidence of DLTs.

The planned duration of treatment is 2 cycles. Patients who are receiving benefit from study drug may continue to be treated with LY3164530 until 1 or more of the criteria for discontinuation have been fulfilled (Section 6.3.1).

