7.2.2.2. DLT-Equivalent Toxicities

A DLT-equivalent toxicity is defined as an AE occurring in Cycle 2 and beyond that would have met the criteria for a DLT if it had occurred during Cycle 1. For individual patients experiencing a DLT-equivalent toxicity, dose adjustments will be made as outlined in Section 7.2.5.

At each interim analysis (as defined in Section 10.10), the rate of DLT-equivalent toxicities will be assessed. If the rate of DLT-equivalent toxicities is unacceptable (eg, a DLT-equivalent toxicity is observed in $>33\%$ patients at a given dose level), then a safety analysis will be triggered and the data will be reviewed by study investigators and the Lilly CRP/CRS. If the findings indicate that a dose level does not have an acceptable safety profile for chronic (Cycle 2 or later) administration, then a lower dose level will be chosen for further investigation. This decision will be documented in writing.

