7.2.2.3. Dose Escalation Method

Dose escalation will be driven by a mTPI method (Ji and Wang 2013) (Attachment 7). A 3+3 design is commonly used in Phase 1 trials due to its simple, intuitive, and pre-specified escalation rules. However, the 3+3 method has been criticized for being conservative because the method is dictated by the observed DLT rate without acknowledging the variability arising from small cohort size.

Like the 3+3 design, the mTPI method incorporates pre-specified escalation rules. In contrast, the mTPI method is based on quantitative models that incorporate uncertainty into the decision

rules, thereby allowing more aggressive dose escalation. In the mTPI method, the number of patients in each cohort is not fixed, but a minimum of 3 patients are required for this study at each dose (unless the rule in the table indicates to deescalate the dose due to unacceptable toxicity [DU]). If 3 to 6 patients are enrolled in a cohort, the escalation rule parallels a traditional 3+3 design. However, the stay/deescalation rule of the mTPI is more aggressive than the 3+3 design. For instance, with 2 to 3 DLTs per 6 patients enrolled, the mTPI would recommend staying at the current dose, whereas the 3+3 design would recommend deescalation. [Figure JNBA.1](#) provides the mTPI escalation rules for any cohort size up to 20 patients.

In [Figure JNBA.1](#), the number of patients dosed at a given dose level are shown in the columns (x-axis), while the number of DLTs experienced are shown in the rows (y-axis). The rules in this figure will be used for each dose level evaluated; the patient numbers and DLTs do not carry over from cohort to cohort. By locating the intersection of the number of patients dosed and the number of DLTs, 1 of 4 pre-defined rules is used:

- E: Escalate the dose
- S: Stay at the same dose
- D: Deescalate the dose
- DU: Deescalate the dose due to unacceptable toxicity. The dose cannot be re-escalated to this dose level at a future point in the escalation.

If agreed upon by the investigators and Sponsor (for instance, if PK/PD data suggest that increasing the dose further is not expected to yield additional benefit), a more conservative rule may be applied. For instance, if the rule indicates “E” to escalate, the dose may remain at the current dose level or be deescalated to a lower level.

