	17																	DU	DU	DU	DU
	18																		DU	DU	DU
	19																			DU	DU
	20																				DU

E = Escalate to the next higher dose
 S = Stay at the current dose
 D = De-escalate to the next lower dose
 U = The current dose is unacceptably toxic
 MTD = 30%
 Equivalence Interval = (28.7%, 30.1%)

Figure JNBA.1. Dose-finding spreadsheet of the modified toxicity probability interval method showing number of patients treated at a given dose vs. number of DLTs observed at that dose .

The beginning dose level for Schedule 1 was 300 mg. The starting dose level for Schedule 2 will be 500 mg. The dose will be escalated by a maximum increment of 100%. If the beginning dose level is determined to be unacceptably toxic, a -1 dose level may be explored.

The exact increment will be determined by the investigators and Lilly CRP/CRS, and may be less than the maximum increment allowed in the protocol. Safety data will be the primary criteria for both the decision to dose-escalate and for selecting the dose to be administered in the next cohort. In addition, if available at the time of the dose escalation decision, PK (maximum serum concentration [C_{max}], area under the serum concentration-time curve [AUC], and CL) and/or PD results will be used as secondary/supporting data for dose escalation. No dose escalation can occur without prior discussion and agreement between the investigator and the Lilly CRP or CRS; the decision will be documented in writing. Inpatient dose escalations are not permitted.

Although an example escalation table is shown in [Table JNBA.3](#), alternate doses may be selected.

Table JNBA.3. Sample Dose Escalation Schema

Dose Level (Cohort)	Schedule 1 Dose	Schedule 2 Dose
-1	100 mg	400 mg
1	300 mg	500 mg
2	600 mg	600 mg
3	1000 mg	700 mg
4	1250 mg	

In Cohort 1 for Schedule 1 only, the first patient is required to complete a full cycle (28 days) before subsequent patients can be dosed. Subsequent patients in Cohort 1 can be dosed concurrently. Beginning with Cohort 2 for Schedule 1 and for all cohorts with Schedule 2, patients within a cohort can be dosed concurrently.

The decision to stop dose escalation will be primarily driven by the appearance of DLTs and the rules in [Figure JNBA.1](#). However, if PK/PD data suggest that increasing the dose further is not expected to yield additional benefit, escalation may cease.

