10.4. Safety Analyses

All patients who have been exposed to LY3164530 will be evaluated for safety and toxicity. Adverse event terms and severity grades will be assigned by the investigator using CTCAE v 4.03.

Safety analyses will include summaries of the following:

- AEs, including severity and possible relationship to study drug
- dose adjustments (reductions, omissions, and delays)
- laboratory values
- vital signs
- DLTs at each dose level
- ECGs
- Extent of concomitant medications.

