10.5. Pharmacokinetic Analyses

Pharmacokinetic analyses will be conducted on patients who have been exposed to study drug and have had samples collected.

Pharmacokinetic parameter estimates for LY3164530 will be calculated by standard noncompartmental methods of analysis.

The primary parameters for analysis will be C_{max} , $AUC_{0-t_{last}}$, $AUC_{0-\tau}$, and $AUC_{0-\infty}$ of LY3164530. Other noncompartmental parameters, such as $t_{1/2}$, CL, volume of distribution (V), and accumulation ratios may be reported. Additional exploratory analyses will be performed if warranted by the data, and other validated PK software programs may be used if appropriate and approved by Lilly Global PK/PD management. The version of any software used for the analysis will be documented and the program will meet the Lilly requirements of software validation.

Pharmacokinetic parameter estimates will be evaluated to delineate effects of dose proportionality and temporal linearity. Log-transformed C_{max} and AUC estimates will be assessed to estimate ratios of geometric means and the corresponding 90% confidence intervals (CIs).

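### The supplied SAP (Version 1) was not brought into line with Amendment (b): it has no weekly schedule, and its PD summaries, PK parameters, review triggers and QTc days differ from the amended protocol

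*Protocol*

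**What the plan says.** **Protocol, as amended.** The primary objective is to "determine an RP2D and schedule of LY3164530" (5.2.1). Schedule 1 doses on Days 1 and 15 and Schedule 2 on Days 1, 8, 15 and 22; "A cycle will consist of 28 days and the schedules will enroll in parallel" (6.2). Section 6.2 also ties the RP2D patient count to a dose and a schedule together.

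On analysis, 10.6 summarises PD and immunogenicity by dose and by schedule. Section 10.5 puts AUC over the dosing interval among the primary PK parameters. Section 10.10 calls for a data review after about 6 patients at a dose level and an interim analysis at 15 or more. Other sections name dose level without schedule: 10.1 ("Data analyses will be provided by dose levels and for all patients combined wherever appropriate"), 10.4 ("DLTs at each dose level") and the DLT-equivalent rule in 7.2.2.2 ("patients at a given dose level), then a safety analysis will be triggered").

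**SAP.** The Revision History lists Version 1 only, approved before first dosing. The objective (4.1) is an RP2D without schedule. The design (5.1) and exposure text (6.13.2) give Days 1 and 15, and the only starting dose is 300 mg (6.13). Section 6.1 repeats the Protocol 10.1 sentence. Section 6.12.1 summarises PD and immunogenicity by dose, with C_max, AUC to the last measurable concentration and AUC to infinity as primary PK parameters. Section 6.15 has a review at about 5 patients and an interim analysis at 10. Section 6.13.7 offers a categorical interval analysis on Days 1 and 15 of each cycle plus the follow-up visit, to be run only if needed.

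**The concern.** The trial must now choose a dose and a schedule. That choice rests on safety, DLT, PK and PD data, so the analysis plan has to keep the schedules apart and cover what was added for the weekly one. A programmer working from the supplied SAP would have no schedule stratum, no AUC over the dosing interval, triggers that differ from the protocol's, and an ECG interval analysis built on Schedule 1 dosing days.

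The triggers matter beyond bookkeeping. Protocol 7.2.2.2 has the DLT-equivalent rate assessed at each interim analysis, so the trigger also settles when that assessment falls due.

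**Working it through.** No sample size, power or error rate is involved. The check sets the two documents side by side and then counts.

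| Item | Protocol | SAP Version 1 |
|---|---|---|
| Objective | RP2D and schedule (5.2.1) | RP2D (4.1) |
| Dosing days | 1, 15 or 1, 8, 15, 22 (6.2) | 1, 15 (5.1, 6.13.2) |
| Starting dose | 300 mg (Schedule 1), 500 mg (Schedule 2) (7.2.2.3) | 300 mg (6.13) |
| PD and immunogenicity | by dose and schedule (10.6) | by dose (6.12.1) |
| Primary PK list | includes AUC over the dosing interval (10.5) | does not (6.12.1) |
| Review trigger | about 6 (10.10) | about 5 (6.15) |
| Interim trigger | at least 15 (10.10) | 10 (6.15) |

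**1. Dosing interval.** Schedule 1: 15 − 1 = 14 days. Schedule 2: 8 − 1 = 7 days. The missing PK parameter therefore covers a period twice as long on one schedule as on the other, and a by-dose row that mixed them would average different quantities.

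**2. Triggers.** The interim triggers differ by 15 − 10 = 5 patients. The RP2D needs 10 to 20 patients at the chosen dose (6.2, 7.2.3). A dose closed with 10 to 14 patients would reach the SAP's interim analysis but not the protocol's.

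**3. ECGs in the conditional interval analysis, Cycle 1.** Count the same-day post-infusion time points (end of infusion, 2 h and 6 h, so 3 per day).
- Attachment 4, Schedule 1: Days 1 and 15, 2 × 3 = 6; outside Days 1 and 15: 0 of 6.
- Attachment 4, Schedule 2: Days 1 and 8, 2 × 3 = 6; outside Days 1 and 15: 3 of 6 (all of Day 8). Day 15 has only a predose single ECG.
- Attachment 1 asks for predose, end-of-infusion, 2 h and 6 h triplicates on the day of dosing in Cycle 1. Read literally, Schedule 2 has 4 × 3 = 12 points, and Days 8 and 22 leave out 2 × 3 = 6 of 12.

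Half is omitted either way, but the counts differ because the attachments differ. Protocol 8.1.3.1 sends the reader to Attachment 1 for the Cycle 1 triplicates, while the Attachment 1 comment itself points to Attachment 4.

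**The case against.** The best defence is that this is a version lag. SAP Version 1 was approved before first dosing and the weekly schedule came later. Attachment 8 lists 10.10 among the revised sections, with the review count moving from 5 to 6. A later SAP may exist; the documents do not show one. That explains the gap but does not close it.

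Some items also carry little weight. Both documents allow further interim analyses and keep the escalation grid in force. The analyses are descriptive. The interval analysis is optional twice over, and SAP 6.13.7 still summarises all ECGs for abnormal findings. Accumulation ratios are no evidence of a gap: the protocol says only that "volume of distribution (V), and accumulation ratios may be reported", and both lists are open-ended. These points stand and limit the consequence.

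A reader might infer something stronger: that the protocol itself pools the schedules, so that 600 mg every 2 weeks and 600 mg weekly share one row and one DLT count. The documents do not support that.
- Section 7.2.2.3 says "the patient numbers and DLTs do not carry over from cohort to cohort" and describes cohorts within schedule: "Beginning with Cohort 2 for Schedule 1 and for all cohorts with Schedule 2, patients within a cohort can be dosed concurrently". It also gives each schedule its own starting dose level.
- Section 7.2.4.2 speaks of the dose levels of Schedule 1, the Introduction states the MTD for the Days 1 and 15 regimen, and 6.2 sets the RP2D count by dose and schedule.
- The closing qualifier in 10.1 leaves room to separate schedules.
- The 600 mg overlap appears only in Table JNBA.3, a sample schema from which other doses may be chosen.

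Nor can one put a figure on a diluted DLT-equivalent rate. The documents give no counts, the 33% is an example, and crossing it prompts a review by people who would know each patient's schedule.

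A general ECG contrast between schedules in later cycles is not secure either. In Cycle 2, Attachment 4 has ECGs on Days 1, 8, 15 and 22 for both, so any contrast depends on which ECGs are counted.

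**Conclusion.** The concern holds for the supplied SAP. It omits Schedule 2 from its objective, design, starting-dose and exposure text, and it departs from the amended protocol on the PD stratum, one primary PK parameter and both triggers. If the interval analysis is run, it leaves out half of the Schedule 2 Cycle 1 same-day post-infusion time points: 3 of 6 by Attachment 4, or 6 of 12 by a literal reading of Attachment 1.

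In the protocol, the unqualified use of dose level in 10.1, 10.4, 10.10 and 7.2.2.2, and the absence of a schedule stratum in 10.5, are loose wording in a document that otherwise treats cohorts as schedule-specific. This is not an instruction to pool, and the escalation decisions are largely protected.

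The conclusion assumes that Version 1 is the operative SAP. If a later version already covers Schedule 2, only the protocol clarification and the reconciliation of Attachments 1 and 4 remain. The discrepancies should be settled before the analyses are programmed; they do not undermine the design.

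**What to change.** Revise the SAP:
- Add Schedule 2 to the objective, design, starting-dose and exposure text (4.1, 5.1, 6.13, 6.13.2).
- Make dose level within schedule the reporting unit for safety, DLT, PK and PD (6.1, 6.12.1, 6.13), with no by-dose row that combines schedules.
- Add AUC over the dosing interval to the primary PK parameters (6.12.1).
- Reconcile the triggers in 6.15 with Protocol 10.10.
- Extend the conditional interval analysis (6.13.7) to every Schedule 2 dosing day with ECGs: Days 1, 8, 15 and 22.

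In the protocol, reconcile Attachments 1 and 4 on the Cycle 1 post-infusion ECGs for Schedule 2. As a minor clarification, state in 10.1, 10.4, 10.5, 10.10 and 7.2.2.2 that dose level means dose level within schedule, consistent with 6.2 and 7.2.2.3.

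The cost is a SAP revision, some protocol wording and new table shells. Some rows will hold fewer patients. No new data or patients are needed.
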